adaptations due to reduced iron efflux during overtraining to aid in the maintenance of physical performance has not been explored.

B3. MILITARY RELEVANCE

This study supports the Military Operational Medicine Research Program's Physiological Health and Performance Program Area under the BPE Work Unit. The BPE Work Unit is intent is to execute basic and applied research aimed at identifying and develop biomedical strategies and solutions that safely and ethically enhance Warfighter physical, cognitive, sensory and behavioral performance in training and operational environments, enabling lethality and overmatch. The proposed work aligns to the Physiological Health and Performance Strategic Plan Technical Challenge 1.1.1.1: Identify pharmacological enhancement protocols improving specific task performance under operational stress.

B4. OBJECTIVES/SPECIFIC AIMS/RESEARCH QUESTIONS

Objective

1. Determine the effects of EPO on hematological adaptions compared to baseline during 4 weeks of overtraining.
2. Determine the time course change in physical performance (time trial) with EPO compared to baseline.
3. Assess the influence of EPO non-hematological adaptation (whole-body and skeletal muscle substrate oxidation and glucose turnover) following 4 weeks of overtraining compared to baseline.

Hypothesis

1. Hemoglobin and hematocrit will be maintained with EPO during 4 weeks of overtraining.
2. Physical performance will be maintained with EPO during 4 weeks of overtraining.
3. EPO will increase whole body and skeletal muscle fat oxidation, and reduce reliance on endogenous glucose store following 4 weeks of physical training.

B5. RESEARCH PLAN

B5.1 Research Design

This study will be a longitudinal trial.

B5.2 Research Subjects/Population(s)

B5.2.1 Subject Population(s)

Subject population will be military or civilians representative of active duty male and female service members, being in good health and recreationally active.

B5.2.2 Number of Subjects, Records, and/or Specimens

A total of 8 volunteers will be required to achieve sufficient statistical power. To complete testing on 8 volunteers, we estimate we will need to enroll 60 individuals. All screening will stop once complete data has been collected on 8 volunteers. Records and specimen collection are described in the Research Procedures and Data Collection sections. During briefings and consenting potential participants will be informed that even though they may be eligible and want

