Study Design Overview: Healthy physically active individuals will be recruited to participate in this longitudinal trial. After baseline assessments of body composition, resting metabolic rate (RMR), $\text{VO}_{2\text{peak}}$ and exercise familiarization; volunteers will complete physical performance and substrate oxidation testing (Figure 3). Physical performance will be assessed using time trial. Substrate oxidation will be assessed by volunteers performing 90-min of steady-state load carriage (30% body mass) exercise on a treadmill at $55 \pm 5\%$ of their $\text{VO}_{2\text{peak}}$. 6-6-[$^2\text{H}_2$] glucose will be used as a tracer to assess glucose turnover. Indirect calorimetry will be used to determine carbohydrate and fat oxidation. Muscle biopsies will be performed to measure muscle glycogen, enzyme activity, and molecular markers of substrate metabolism before, immediately after, and 3-hrs post exercise. Multiple blood samples will be collected on substrate oxidation protocol days. To minimize carry over effects of muscle biopsies on subsequent exercise performance, volunteers will not exercise for 3 days. During the first two days of this period, volunteers will undergo carbon monoxide (CO) rebreathing to measure Hgb mass and blood volume. Volunteers will then receive EPO injections 3 times a week for 4 weeks. During the injection period all volunteers will have safety blood draws to assess Hct once a week. Volunteers will also complete a physical performance test once a week to determine time course change in performance with EPO compared to baseline. Exercise training will be controlled during the injection phase, consisting of a combination of endurance- and resistance-type exercise. During the final week of the injection phase body composition, resting metabolic rate (RMR) and $\text{VO}_{2\text{peak}}$ will be reassessed. At the end of the 4-week injection phase volunteers will complete a final physical performance test and substrate oxidation protocol, followed by two CO rebreathing tests on subsequent days. All food and beverages (except water) will be provided to volunteers beginning at the pre injection physical performance and substrate oxidation through the duration of the study. All data collection will occur at USARIEM.

Figure 3: Study Timeline

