$\dot{V}O_2$ peak (credentialed procedure): Following an overnight fast (10 hrs), volunteers will complete a maximal aerobic exercise sessions to determine peak oxygen uptake ($\dot{V}O_2$ peak) on a treadmill. $\dot{V}O_2$ peak will be determined using an indirect, open circuit respirator system (Parvomedics). Volunteers will be clothed in appropriate athletic attire and perform this assessment at standard ambient indoor temperature (20-22°C) and humidity conditions (30-80%). Volunteers will be given adequate time to become familiar with the testing procedures and allowed a 3-min self-paced warm-up on the treadmill. At the start of testing, the volunteer will put on a nose clip and a mouthpiece or face mask connected to a 2-way respiratory valve, which is attached to a head piece to hold it in place. The volunteers will begin by running for 4 min at a pace predetermined as comfortable at a 0% grade. At 4-min, the grade will be increased to 4% followed by an additional 2% every 2 min thereafter until volitional exhaustion. Assessment of $\dot{V}O_2$ peak will be done before and during the last week of the injection phase. Changes in $\dot{V}O_2$ peak after injections will be taken into account to adjust the speed and grade of the treadmill during steady-state load carriage exercise.

Heart rate will be monitored throughout exercise using a heart-rate monitor (Polar Electro Inc, Oulu, Finland), and record during the last 30 seconds of each workload during all testing. The test will be stopped immediately if the subject reports angina-like symptoms, exertional syncope, shows signs of poor perfusion (i.e., light-headedness, confusion, ataxia, pallor, cyanosis, nausea, or cold and clammy skin), or if testing equipment fails. Study personnel conducting maximal aerobic testing will be credentialed and listed on the DOA log with code "J."

Resting Metabolic Rate (non-credentialed procedure): Following a 10 hr overnight fast, RMR will be measured using open circuit indirect calorimetry (True Max 2400, Parvomedics, Sandy, Utah, USA) at baseline. Volunteers will rest in the supine position for approximately 30-min before measurement in a quiet and dim, temperature regulated room. To minimize error, volunteers will be instructed to minimize

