Study Exercise (non-credentialed procedure): During the injection phase volunteers will conduct prescribed exercise training 4 days and 1 day of physical performance testing (time trial) per week. Volunteers will perform both weighted (treadmill or outdoor; walking, running, and load carriage) and unweighted (cycle ergometry) endurance-type exercise, and resistance-type exercise throughout the protocol. Exercise will be metabolically matched between groups, with exercise-induced energy expenditure being 1000-1500 kcal per day. Prescribed endurance-type exercise will be low-to-high intensity (30-85% $\dot{V}O_2$ peak) using the ACSM metabolic equations for steady-state exercise (37) and the compendium of metabolic equivalents for physical activities. This level of training is similar to that conducted during arduous military training in garrison (38). $\dot{V}O_2$ peak will be assessed after 2 weeks into the injection phase. Exercise intensity will be adjusted based on alterations in $\dot{V}O_2$ peak. Study personnel conducting exercise will be listed on the DOA log with code "V."

Load Carriage Exercise (non-credentialed procedure): Volunteers will complete 90-min of weighted steady-state exercise on a treadmill at $55 \pm 5\%$ of their $\dot{V}O_2$ peak, with 30% of volunteer's body mass. The speed and grade of the treadmill will be determined using the ACSM metabolic equation for walking based on desired $\dot{V}O_2$ (39). Prior to the protocol day, participants will perform a practice session of the treadmill exercise to confirm the prescribed speed and grade are appropriate to induce target $\dot{V}O_2$. The treadmill speed and grade will be maintained for both arms of the study to match the absolute workload of the exercise across treatments. Study personnel conducting treadmill load carriage will be listed on the DOA log with code "V."

Carbohydrate Tracer Study (credentialed procedure): Following an overnight (10 hour) fast, two catheters will be placed into the lower arm (one in each arm). One arm will be used for infusion of 6,6-[2 H₂] glucose tracer and the other will be used for blood sampling. Following an initial blood sample collection to determine background enrichments, a primed, continuous infusion of 6,6-[2 H₂] glucose will begin (prime, 82.2 $\mu\text{mol}\cdot\text{kg}^{-1}$; continuous rate, 0.78 $\mu\text{mol}\cdot\text{kg}^{-1}\cdot\text{min}^{-1}$, **Figure 4**). The 6,6-[2 H₂] glucose will

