Carbohydrate, fat, and protein oxidation rates will be calculated from $\dot{V}O_2$ (L/min) and $\dot{V}CO_2$ (L/min) during the 90-min exercise bout as described by Jeukendrup and Wallis (45):

$$\begin{aligned} \text{Fat oxidation (g/min)} &= 1.695 \times \dot{V}O_2 \text{ (L/min)} - 1.701 \times \dot{V}CO_2 \text{ (L/min)} \\ \text{Total carbohydrate oxidation (g/min)} &= 4.585 \times \dot{V}CO_2 \text{ (L/min)} - 3.226 \times \dot{V}O_2 \text{ (L/min).} \end{aligned}$$

Muscle Glycogen

Glycogen concentration will be determined using ~3 mg (dry weight) freeze dried muscle homogenized in water using a TissueLyser II with a 5-mm steel bead (Qiagen, Valencia, CA, USA). Homogenates will be boiled at 100°C for 5 min and centrifuged at 13,000×g for 5 min at room temperature. Supernatant will be removed and muscle glycogen concentrations will be assessed using an endpoint colorimetric assay (Cat# MAK016; Sigma-Aldrich, St. Louis, MO, USA).

Immunohistochemistry

Resting fasted muscle samples before and after EPO dosing will be frozen for cross-section analysis to include but not limited to fiber typing. Muscle sections will be stained with antibodies against either myosin heavy chain I or myosin heavy chain IIA. Sections will then be incubated with appropriate conjugated secondary antibodies for one hour at 37 °C (Alexa Fluor-568, Molecular Probes, Life Technologies). Fluorescent-conjugated (AlexaFluor488) Wheat Germ Agglutinin (WGA) will be used to stain the extracellular matrix for the calculation of fiber cross-sectional area using Image J software.

mRNA, microRNA, and c-microRNA Expression

Total RNA will be isolated using ethanol precipitation from approximately 20 mg of muscle. Quantity and quality of RNA will be assessed using a Nanodrop ND-1000 spectrophotometer (Nanodrop, Wilmington, DE, USA). Equal amounts of total RNA will be synthesized into cDNA for analysis of mRNA (iScriptTM

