5.7.1.1 FDA-approved device being used in this research according to the approved labeling

DEXA, DPX-IQ, Lunar Corporation, True Max 2400, Parvomedics, Sandy, Utah, USA, Polar Electro Inc, Oulu, Finland

5.7.1.2 FDA-approved device being used in this research in a manner other than its approved labeling: N/A

B5.7.2 Drugs

B5.7.2.1 FDA-approved and used in accordance with the approved labeling

B5.7.2.2 FDA-approved and used in a manner not in accordance with its approved labeling:
PROCRIT, EPOETIN ALFA, Janssen Products, LP, Titusville, NJ, USA

B5.7.2.3 Any drug not approved by the FDA: N/A

B5.8 Statistical Analysis

B5.8.1 Sample Size Estimation

Based on results for multiple outcomes across different studies (**Table 4**) a sample size of 8 is required to statistical significance.

Table 4: Previous study effect sizes

Study	Outcome	Delta	Effect Size	Sample Size
Thomson et al. (18)	TTE	10 ± 6	1.40	7
Plenge et al. (24)	Hct	5.1 ± 3	1.56	7
Caillaud et al. (19)	CHO Oxidation	0.7 ± 0.3	1.24	4
Caillaud et al. (19)	Fat Oxidation	0.2 ± 0.05	3.51	2

B5.8.2 Data analysis

Statistical analyses will be conducted using either SPSS (IBM Corp. Armonk, NY), SAS 9.3 (SAS Institute Inc., Carey, NC), or equivalent. Common descriptive statistics will be used to describe volunteer characteristics. Shapiro-Wilk tests will be used to determine normality of data. Paired t-tests will be used to assess phase effects (PRE vs. POST injection) for glucose turnover, and substrate oxidation. Repeated measures ANOVA will be used to assess main effects of time for physical performance. Mixed-model repeated measure ANOVA will be used to assess main effects of phase (PRE vs. POST injection), time and their interaction for blood analytes and muscle molecular analysis. If interactions are significant, appropriate post-hoc correction will be used to examine these relationships. Correlation coefficients and multiple regression analysis will be used to evaluate relationships between study outcome measures. The alpha level will be adjusted for multiple comparisons, with the level for statistical significance set at $P < 0.05$.

SECTION C: HUMAN RESEARCH PROTECTIONS

C1. RECRUITMENT AND CONSENT

C1.1 Identification and Selection of Subjects

Volunteers will be recruited from the federally and non-federally employed civilian population, the Natick Human Research Volunteer (HRV) Pool, and NSSC active duty military personnel.

C1.2 Recruitment Process

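### Fat and carbohydrate oxidation are tested PRE vs POST only as g/min, with no account of exercise VO2, and the plan does not secure equal VO2 in the two sessions

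*Protocol*

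**What the plan says.** Hypothesis 3 (Protocol B4) has two clauses: "EPO will increase whole body and skeletal muscle fat oxidation, and reduce reliance on endogenous glucose store". To test it, each volunteer completes one load-carriage session before and one after the injection phase, "performing 90-min of steady-state load carriage (30% body mass) exercise on a treadmill at" 55 ± 5% of VO2peak (B5.3, Study Design Overview). VO2 and VCO2 are read six times per session.

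B5.4 (Calculations of Carbohydrate and Fat Oxidation) turns those readings into "Fat oxidation (g/min" and "Total carbohydrate oxidation (g/min". No other scale is given. The analysis in B5.8.2, repeated in the SAP, is: "Paired t-tests will be used to assess phase effects (PRE vs. POST injection) for glucose turnover, and substrate oxidation". Neither document plans an exchange ratio, a percentage of energy, a rate per litre of oxygen or a VO2 covariate.

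B5.3 gives two rules for the POST workload. The VO2peak paragraph says that changes in VO2peak after the injections are "taken into account to adjust the speed and grade of the treadmill during steady-state load carriage exercise". The Load Carriage Exercise paragraph says: "The treadmill speed and grade will be maintained for both arms of the study to match the absolute workload of the exercise across treatments". That sentence speaks of arms and treatments in a single-group study. Read as PRE and POST, it fixes speed and grade.

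**The concern.** An absolute rate mixes two things: how much work the volunteer did, and which fuel supplied it. Hypothesis 3 concerns the fuel, at least in its second clause. If VO2 differs between sessions, g/min changes even when fuel selection does not. If VO2 is lower at POST, a real shift towards fat can vanish from the fat g/min comparison.

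There is no control group to absorb a PRE-POST difference in VO2. A difference scattered at random over the volunteers mainly adds variance. One shared by most of them, as when speed and grade follow a rise in VO2peak, moves the mean and so biases the test.

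**Working it through.** **Inputs from the documents.** Fat (g/min) = 1.695 × VO2 − 1.701 × VCO2. Carbohydrate (g/min) = 4.585 × VCO2 − 3.226 × VO2 (B5.4). Target 55% of VO2peak, band 50-60% (B5.3). n = 8. Planning differences: fat 0.2 ± 0.05 and carbohydrate 0.7 ± 0.3 (Protocol Table 4; SAP Table 1).

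**Assumptions.** VO2peak is 3.5 L/min. The exchange ratio R = VCO2/VO2 is 0.85 or 0.88. The Table 4 differences are in g/min, and the ± figures are SDs of the paired change; the table states neither. Tests are two-sided at 0.05.

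**Planning figure.** The smallest effect size in Table 4, 1.24, gives 78% power with 7 volunteers and 85% with 8 in a paired t-test. The total of 8 is therefore reproduced at an assumed 80% power. Nothing below depends on it except the value n = 8.

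**Step 1: scaling.** Put VCO2 = R × VO2:

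- Fat = VO2 × (1.695 − 1.701R)
- Carbohydrate = VO2 × (4.585R − 3.226)

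At fixed R, both rates change by the same percentage as VO2. At R = 0.85 the multipliers are 0.249 and 0.671 g per litre of oxygen. At R = 0.88 they are 0.198 and 0.809.

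**Step 2: speed and grade follow VO2peak.** VO2 at 55% is 0.55 × 3.5 = 1.925 L/min. At R = 0.85 this gives fat 0.480 and carbohydrate 1.292 g/min. VO2 then rises in step with VO2peak:

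| Assumed VO2peak gain | Fat change, g/min | Share of 0.2 | Carbohydrate change, g/min | Share of 0.7 |
|---|---|---|---|---|
| 5% | 0.024 | 12% | 0.065 | 9% |
| 10% | 0.048 | 24% | 0.129 | 18% |

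Fuel mix is unchanged throughout. If the fat shift is common to all 8 volunteers and the SD is 0.05, the noncentrality is √8 × 0.024/0.05 = 1.36 or √8 × 0.048/0.05 = 2.71. The test then gives P<0.05 in about 22% or 65% of trials, against a nominal 5%. The SD matters: the stated effect size of 3.51 implies 0.2/3.51 = 0.057, and the figures become about 18% and 54%. For carbohydrate with SD 0.3 they are about 8% and 18%.

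**Step 3: speed and grade stay fixed.** What remains is drift in VO2, since the load is 30% of body mass and both mass and walking economy may change over four weeks of training. At R = 0.88, VO2 of 1.925 L/min gives fat 0.381 and carbohydrate 1.557 g/min. An assumed 2-5% drift gives:

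- Fat 0.008-0.019 g/min, or 4-10% of 0.2
- Carbohydrate 0.031-0.078 g/min, or 4-11% of 0.7

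**Step 4: the extreme.** One session at 50% and the other at 60% of an unchanged VO2peak raises both rates by 60/50 − 1 = 20%. At R = 0.85, fat goes from 0.436 to 0.523 and carbohydrate from 1.175 to 1.410 g/min.

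**Step 5: masking.** In the reverse extreme, 60% to 50%, a real fall in R from 0.85 to 0.821 leaves fat at 0.523 g/min in both sessions. Per litre of oxygen, fat rises from 0.249 to 0.299 (+20%), so the shift is visible on the ratio scale but not in g/min.

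**The case against.** The strongest case against this point has five parts.

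- **The workload may already be matched.** The Load Carriage Exercise paragraph fixes speed and grade and requires a practice session to confirm the target VO2. If it governs, a gain in VO2peak lowers the percentage of VO2peak but need not change VO2 in L/min. This stands, and only the small drift of Step 3 is left. The VO2peak paragraph says otherwise, however, so the plan as written does not secure equal VO2.
- **The band alone proves little.** A reader might infer that 55 ± 5% lets the results swing by 20%. The documents do not support that as an expected bias: all volunteers would have to move from one edge to the other in the same direction. A reader might also infer that a few mismatched volunteers could decide the result. Nothing calculated here shows that, because the rejection rates in Step 2 assume a shift common to all eight.
- **The artefact does not imitate the whole hypothesis.** At fixed R, fat and carbohydrate rise together, while Hypothesis 3 predicts more fat and less reliance on glucose. Reading both results side by side would give a warning. This stands, but no such check is planned.
- **g/min is a legitimate outcome.** It directly measures the first clause of Hypothesis 3, and tracer turnover and muscle glycogen also bear on the second. A reader might infer that g/min is the wrong scale and must be replaced; the documents do not support that.
- **The ratio is not immune.** It can vary with relative intensity. In the 50% to 60% case, a rise in R from 0.85 to only 0.874 would cancel the whole increase in fat g/min. The ratio removes the scaling with VO2, not every effect of intensity. That argues for reporting both scales.

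**Conclusion.** The point holds as a modest gap in the analysis plan. g/min is an acceptable outcome, but on its own, without exercise VO2, it cannot separate a change in workload from a change in fuel use.

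Its size depends on an unresolved conflict in B5.3. It is about 12-24% of the fat planning difference and 9-18% of the carbohydrate one if speed and grade follow an assumed 5-10% VO2peak gain. It is roughly 4-11% of either if they stay fixed and VO2 drifts by an assumed 2-5%. These figures rest on an assumed VO2peak of 3.5 L/min, ratios of 0.85 and 0.88 respectively, and Table 4 read as g/min. The gain in VO2peak and the drift are assumptions too; the documents give no value for either.

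It does not follow that a positive fat result would be an artefact, or that the plan cannot test Hypothesis 3.

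**What to change.** In Protocol B5.8.2 and the SAP:

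1. Keep g/min as the outcome for the clause that fat oxidation will increase.
2. Prespecify a PRE-POST comparison of the exchange ratio, or of the percentage of energy from fat and carbohydrate, averaged over the exercise readings. Name which of the six readings enter the average.
3. Report mean exercise VO2 for both sessions beside these results.
4. State that a shift in fuel use will be claimed only if the ratio supports it.

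Separately, reconcile the VO2peak and Load Carriage Exercise paragraphs of B5.3, so that the intended PRE-POST contrast in workload is known before the data are seen.

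The cost is wording. VO2 and VCO2 are already collected, and the sample size does not change. There are two downsides: one more comparison falls under the planned multiplicity adjustment, and the ratio must be interpreted with relative intensity in mind.

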5.7.1.1 FDA-approved device being used in this research according to the approved labeling

DEXA, DPX-IQ, Lunar Corporation, True Max 2400, Parvomedics, Sandy, Utah, USA, Polar Electro Inc, Oulu, Finland

5.7.1.2 FDA-approved device being used in this research in a manner other than its approved labeling: N/A

B5.7.2 Drugs

B5.7.2.1 FDA-approved and used in accordance with the approved labeling

B5.7.2.2 FDA-approved and used in a manner not in accordance with its approved labeling:
PROCRIT, EPOETIN ALFA, Janssen Products, LP, Titusville, NJ, USA

B5.7.2.3 Any drug not approved by the FDA: N/A

B5.8 Statistical Analysis

B5.8.1 Sample Size Estimation

Based on results for multiple outcomes across different studies (**Table 4**) a sample size of 8 is required to statistical significance.

Table 4: Previous study effect sizes

Study	Outcome	Delta	Effect Size	Sample Size
Thomson et al. (18)	TTE	10 ± 6	1.40	7
Plenge et al. (24)	Hct	5.1 ± 3	1.56	7
Caillaud et al. (19)	CHO Oxidation	0.7 ± 0.3	1.24	4
Caillaud et al. (19)	Fat Oxidation	0.2 ± 0.05	3.51	2

B5.8.2 Data analysis

Statistical analyses will be conducted using either SPSS (IBM Corp. Armonk, NY), SAS 9.3 (SAS Institute Inc., Carey, NC), or equivalent. Common descriptive statistics will be used to describe volunteer characteristics. Shapiro-Wilk tests will be used to determine normality of data. Paired t-tests will be used to assess phase effects (PRE vs. POST injection) for glucose turnover, and substrate oxidation. Repeated measures ANOVA will be used to assess main effects of time for physical performance. Mixed-model repeated measure ANOVA will be used to assess main effects of phase (PRE vs. POST injection), time and their interaction for blood analytes and muscle molecular analysis. If interactions are significant, appropriate post-hoc correction will be used to examine these relationships. Correlation coefficients and multiple regression analysis will be used to evaluate relationships between study outcome measures. The alpha level will be adjusted for multiple comparisons, with the level for statistical significance set at $P < 0.05$.

SECTION C: HUMAN RESEARCH PROTECTIONS

C1. RECRUITMENT AND CONSENT

C1.1 Identification and Selection of Subjects

Volunteers will be recruited from the federally and non-federally employed civilian population, the Natick Human Research Volunteer (HRV) Pool, and NSSC active duty military personnel.

C1.2 Recruitment Process

For Soldiers in the U.S. Army Natick Soldier System Center Human Research Volunteer (HRV) Program, the Principal Investigator will furnish a copy of the consent form to the Human Research Volunteer Program Coordinator or designee. The Coordinator will schedule the consent briefing for the HRV platoon.

Superiors of Service members (e.g., unit officers, senior NCOs, and equivalent civilians) shall not be present at any recruitment sessions or during the consent process in which members of units under their command are afforded the opportunity to participate as human subjects of research.

Civilian volunteers and other active duty personnel will be recruited by “word of mouth”, posted flyers (“off-site recruitment flyer” to be used for any flyers posted outside of NSSC, “recruitment flyer” to be used for postings within NSSC), or electronic distribution of the “off-site” flyer to include a text-only, approved version of the flyer. Recruiting materials will be distributed around NSSC, surrounding community, and on bulletin boards at local universities. The text-based flyer will be posted on various USARIEM social media sites and used in distribution media requiring a text format (e.g., electronic newsletters). Recruiting may also be conducted through briefings presented to college classes, clubs, sports teams, or other organizations. Approvals from the requisite parties will be obtained prior to any recruitment activities.

Principal Investigator or Project Coordinator will receive and respond to inquiries submitted from these recruitment materials, and will schedule informed consent briefings for these potential volunteers. An ombudsman (indicated by code “L” on the DOA Log) will be present for HRV briefings. All civilian and non-HRV Soldier briefings will be done one-on-one.

C1.3 Eligibility

Volunteers will be medically cleared by the OMSO before participation in accordance with USARIEM procedures outlined for screening volunteers for research involving exercise, tracer infusions, muscle biopsies and EPO use at USARIEM. In addition, volunteers will be screened for problems with blood clotting, including prothrombin time (PT)/ partial thromboplastin time (PTT), which is a specific criterion for research involving muscle biopsies. Health problems identified during the screening process will be documented and a copy provided to the volunteer. The volunteer will be encouraged to make an appointment with their primary care provider for a full evaluation of the problem. Volunteers with evidence of any physical, mental, and/or medical conditions that would make the proposed studies relatively more hazardous will be excluded. Any personal health information collected during this screening process will be destroyed at the time of study withdrawal or at the completion of the study.

All volunteers must be willing to consume only food and beverages provided by study staff during the entire study. Additionally, volunteers must be willing to refrain from any additional exercise during the study.

C1.4 Consent Process

Informed consent documents will be provided to each prospective volunteer. Additionally, an oral presentation will be provided to prospective volunteers by the principal investigator or his designee. In case of COVID risk mitigation plans, briefings can be done virtually and consent forms can be emailed and digitally signed. The purpose of this study, procedures involved, risks, and expectations of volunteers will be explained. The principal investigator or designee will answer all group and private

questions. Potential volunteers will have a minimum of an hour, but can take longer, to review the consent form. Interested volunteers will sign the informed consent form prior to undergoing initial screening. If they meet all the medical selection criteria after completing the screening health assessment they will be scheduled to begin data collection. A copy of the informed consent will be provided to the volunteer with the original kept for study documentation. No study procedures will occur prior to the volunteer giving informed consent. Volunteers who have already consented will be informed of any new information or changes to the protocol that may affect their willingness and ability to continue participation in the study using an approved consent addendum.

C1.4.1 Research involving subjects with cognitive impairment or who lack capacity to provide informed consent

N/A

C1.4.2 Research involving non-English speaking subjects

N/A

C1.4.3 Research involving a waiver of the requirement to obtain informed consent OR alteration of the elements of informed consent

N/A

C1.4.4 Research involving a waiver of the requirement for investigator to obtain a signed consent form

N/A

C1.4.5 Waivers of assent or parental permission when the research involves children

N/A

C2. COMPENSATION FOR PARTICIPATION

Military and civilian personnel will receive \$50 for each successful blood draw. There are 26 blood draws during the entire study. Volunteers completing all draws will receive \$1300. If a volunteer does not complete the entire study, they will be compensated for the number of successful blood draws they did complete. If USARIEM staff fail to get a blood draw and the volunteer completes the study they will be compensated in full. Volunteers will not be eligible for any other form of compensation during this study.

Note: Participants who receive more than \$600 in a calendar year will have this income reported to the Internal Revenue Service.

C3. WITHDRAWAL FROM RESEARCH PARTICIPATION

Volunteers will be allowed to withdraw at any time without penalty or loss of benefits to which they would otherwise be entitled. They will do so by informing the PI, AI or a staff member of their intent to withdraw verbally or in writing (electronic or paper/pencil). They will then be asked to verbally discuss their choice to withdraw with the PI so that reasons for withdrawal can be documented. An investigator may stop an individual's participation in the study if the volunteer is unwilling or unable to complete study procedures. An investigator may also withdraw a volunteer if the individual becomes ill or injured or it would not be in the volunteer's best interest to continue. If the participant is withdrawn by the investigator or decides to

voluntarily withdraw him/herself, all further data collection will discontinue. Any samples or data collected prior to withdrawal will be maintained. Participants will be compensated for any blood draws they completed up until that point, and they will be asked to return any remaining food items that were provided, in addition to any wrappers and diet/activity logs that they had completed up to the point of withdrawal.

C4. PRIVACY FOR SUBJECTS

To protect the volunteer's privacy, all of their research-related records will be labeled or "coded" with an assigned research volunteer number that will not include their name or any other form of identifiable information. The principal investigator or project coordinator will keep the link between volunteer number and the volunteer's research records in a locked cabinet. Any documents that will require the volunteer's name, such as the consent form, will be kept in a locked cabinet separate from any research documents that contain the volunteer's ID number. The principal investigator and project coordinator are the only people who will be able to match the research volunteer number with any of their personal identifying information.

When the results of the research are published no information will be included that would reveal the volunteer's identity to others. Photographs, videos, or audio-tape recordings of volunteers will only be used, if the volunteer grants permission through the Audio/Visual Image Release form. Each volunteer will also be asked to grant permission for his/her name to be included on his/her photo or video image or in writing connected to his/her image. If a volunteer does not grant permission through the Audio/Visual Image Release, then no photos or other visual recordings will be taken of him/her. In the event that it is discovered that an individual has been inadvertently photographed or visually recorded without his/her permission, the materials will be immediately destroyed. Permission through the Audio Visual Image Release form will be confirmed before any photographs or other visual recordings are used.

C5. CONFIDENTIALITY PROCEDURES FOR RESEARCH RECORDS, DATA, HUMAN BIOLOGICAL SPECIMENS

Complete confidentiality cannot be promised to military participant because information bearing on the military participant health may be required to be reported to appropriate medical or command authorities.

All data and medical information obtained will be considered privileged and held in confidence. Study volunteers will be assigned unique subject identification (ID) numbers that will not contain any personal identifiers such as name, social security number, address, date of birth, zip code, etc. This study subject ID number will be used on all data collection instruments, to include questionnaires, data collection forms, computer records, etc. A number will be assigned as each volunteer is medically cleared for participation. A master list linking the volunteers' names and ID numbers will be kept in a separate locked file in the principal investigator's office, or kept in a computer file with password-protected access restricted to the principal investigator and project manager. The master list linking subjects with their data will be destroyed when the study is closed. When the results of the research are published or discussed in conferences, no information will be included that would reveal identity. Study samples will be processed on site at USARIEM. All samples will be stored using the subject identification number. Samples will be shipped for analysis to Metabolic Solutions. Remaining samples will be stored at USARIEM in a -80°C freezer in room 322 or 304. The volunteers name or other identifiable information will not be included on any data, data collection sheets, specimens, or other research records. De-identified samples will be maintained indefinitely.

Only personnel assigned to the research study by the principal investigator will have access to the data. Hard copy data records will be stored for a minimum of three years from the time the study is completed. Electronic data records will be maintained for a period of at least ten years after the study has been completed.

C6. RISKS OF HARM, MEASURES TO REDUCE THE RISKS OF HARM, AND BENEFITS OF PARTICIPATION

C6.1 Risks of Harm

Research Procedure Name: Dual energy X-ray absorptiometry (DEXA) scan

Research Procedure Description: Volunteer will lay face-up on the DEXA densitometer table in shorts, t-shirts, and stocking feet. Volunteers will be asked to remain motionless for the 8-10 min scan.

Research-related Risks: Exposure to less than 0.6 mrem X-irradiation in a slow-speed (up to 20 minutes) whole-body scan is possible. This dose is equivalent to approximately 1/500 of normal annual background radiation (300 mrem/year), 1/6 of the radiation received in a transatlantic flight (3.825 mrem), or 1/3 of the radiation received in a chest X-ray (2 mrem). The American College of Obstetricians stated that exposure to less than 5 rem (50 mSV) has not been associated with an increase in fetal anomalies or pregnancy loss.

Measures to Minimize Risks of Harm: A quality assurance check will be completed on the DEXA each day prior to its use; the software will not allow the use of the DEXA densitometer if the quality assurance check fails. Volunteers must be advised that the health effects of very low level exposures to ionizing radiation, if any, are unknown (thought to be minimal). Pregnant women may not undergo this procedure. Women of child bearing age must have a documented negative pregnancy test within the 48 hours preceding the scan. Volunteers will be cautioned against becoming pregnant while participating in the study. Study personnel conducting body composition will be credentialed for such procedures and listed on the DOA log with code "U."

Research Procedure Name: Indwelling Catheters

Research Procedure Description: A needle will be used to guide a catheter into the antecubital vein of the volunteer. The catheter will be attached to saline to keep the line patent for multiple blood draws.

Research-related Risks: The risks of blood sampling are small and usually limited to local bruising or swelling. Also sometimes volunteers feel faint or may faint. If the volunteer has had problems with fainting during blood draws in the past, they may be more prone to them during future procedures. If the catheter, the tube that is left in the arm after the needle is removed, becomes clogged at any time during the protocol, we will have to replace this to continue blood sampling. This will require another needle to be inserted into your arm. In addition, the catheter can cause irritation, bruising, swelling, infection, or an allergic reaction.

